## **16.4 INTERIM-ANALYSES**

The primary aims of the two trials will be monitored according to a group sequential plan.

[figure not shown]
### **16.4.1 Group 1 "RISK" patients**

The data will be monitored a total of 5 times in equally spaced intervals, i.e. after the response evaluation at week 12 of 20%, 40%, 60%, 80% and 100% of the total sample size.

Early stopping will be implemented either to reject the null hypothesis of no difference between the two randomized arms, or to retain the null hypotheses. The design of the stopping boundaries is due to O'Brien-Fleming using the normal approximation of the binomial distribution.

### **16.4.2 Group 2 "LOW RISK" patients**

The data will be monitored 5 times i.e. after 20%, 40%, 60%, 80% and 100% of the total number of events (see 13.4.1.2: Power Considerations) This schedule of interim analyses allows an equal distribution of the information between the interim analyses. Early stopping will be implemented either to reject the null hypothesis of no difference between the two randomized arms or to retain the null hypotheses. The design of the stopping boundaries is according to O'Brien-Fleming.

**Figure 6: Design of the stopping boundaries**

The O'Brien and Fleming boundary requires very strong evidence at the first interim analyses, whereas the criteria at the final test are rather close to those for a single sample design. The first opportunity for early stopping in favor of the null hypothesis will be at the second interim analyses.

In case the outer boundary is crossed during one interim analysis in one of the two trials the alternative hypothesis is accepted. If the inner boundary is crossed during one interim-analysis, enough evidence is collected to retain the null hypotheses of no difference between the two randomized arms in terms of the primary endpoint. In this case no ethical reason exists, which forces the closure of the trial. The results of the trial will be discussed by the study committee together with the independent statistical reviewers of the Institute of Medical Statistics and Documentation in Mainz. The decision to stop or continue the trial will include considerations on long term outcome, such as survival, reactivation and permanent consequences as well as toxicity. If it is decided to stop one trial because of futility, it is anticipated that the trial will be continued until the start of the subsequent trial.

## **16.5 POWER CONSIDERATION**

### **16.5.1 Group 1 “RISK” patients:**

The estimated proportion of non-responder in the control group is 50 %. With Arm B (with the addition of MTX) we aim to reduce the rate of non-response to 30%. To achieve a power above 80% we will need a total sample size of 202 patients to show this 20%-difference (two-sided  $\alpha=5\%$ . NQuery 3.0, Fisher’s exact test). The group sequential design of the study will raise the maximum sample size to 228. If the null hypothesis is true, the expected sample size will be reduced to 143 patients. If the alternative hypothesis is true (i.e. a 20% difference in the proportion of non-responders between the two arms) the expected sample size is 158 patients.

In LCH-II we observed an average annual recruitment of 70 – 80 multi-system patients, of whom 60 % had risk organ involvement. This means that 42 – 48 patients will be eligible for randomization of arm A versus arm B . If the randomization rate is similar to LCH II i.e. 85% we will have approximately 35-40 randomizations a year. We assume that we will not be able to evaluate response at week 12 in 10 % of the patients because they will be lost to follow up. This means that we expect to reach the maximum sample size of 228 evaluable patients after a period of approximately 6 years. If the null hypothesis is true, the expected duration of the study will be 4.3 years. If the alternative hypothesis is true, this will be 4.7 years.

### **16.5.2 Group 2 “LOW RISK” patients:**

Data from the previous LCH-II study indicate that the reactivation free survival rate of the control group (LR 6) is approximately exponential distributed with a 1-year reactivation free survival rate of about 65%. With this study we aim to show a 20% difference in the 1-year reactivation free survival rate (i.e. a 1-year reactivation free survival rate of 85% in patients with 12 month continuation treatment) with sufficient power.

To show a 20% difference at the 5% significance level with a power of 80% we would need a total of 36 events following the group sequential design (Jennison Turnbull).

85% of the patients with multi-system LCH without involvement of risk organs had an initial response. That means that with the expected annual recruitment of 40 multi-

[figure not shown]
system patients without risk organ involvement we can expect 34 patients per year who will be eligible for randomization. We expect that 85% of these patients will be randomized this means there will be 29 randomizations/year. About 5% of these patients will show a reactivation within 24 weeks of treatment, another 10% will possibly be lost to follow up within the first 24 weeks. Thus we will be able to recruit about 24 patients/year who will enter the analyses.

We considered a cautious estimated lost to follow up-rate in the calculation, which is assumed to be exponentially distributed with  $\lambda=0.664$ , i.e. about half of the patients are followed for more than one year. Given this lost to follow up rate and a minimum follow up of 2 years (period from entry of the last patients to the final analysis) following the group sequential design, we will need a recruitment period of about 6 years and a maximum sample size of 148 patients.

## **16.6 STOPPING RULES**

In patients without “RISK” organ involvement experience from LCH-II indicate that only a limited number of toxicities can be expected. Therefore for this subgroup no stopping rules will be implemented. Stopping rules for organ toxicity and early deaths are implemented only for patients with “RISK” organ involvement. In LCH patients the differentiation between treatment related toxicity and disease related organ dysfunction (liver, hematopoiesis, mucous membranes and skin) may present a diagnostic dilemma. For this reason organ dysfunction will be assessed according the WHO toxicity score already at diagnosis and throughout the follow up. Clear toxic events should be reported immediately. Interim analyses on severe organ toxicity (WHO score grade III-IV) within the first 12 weeks of therapy will be performed twice a year. The rate of severe organ toxicity within the first 12 weeks of therapy of both treatment arms will be compared by Fisher’s exact test. A group sequential design according to Pocock will be applied to account for repeated significance testing to assure an overall significance level of  $\alpha = 5\%$ . In addition we will monitor early deaths within the first 6 weeks of therapy. In arm A of the LCH II study, 5 early deaths within 12 weeks of therapy were observed among 50 patients (10%, 95% CI 5% – 23%). Based on this previous experience, we consider an early death rate below or equal to 10% as acceptable. An early death rate of 15% as unacceptably high. We will perform Wald’s sequential ratio test. The upper boundaries

we will use will be shown in figure 7.

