## **16.3 ANALYSES**

The analyses of the primary and secondary endpoints will be done according to the intention-to-treat principle, i.e. the patients will be analyzed in their allocated treatment group, even in case of non-compliance or protocol violations.

The statistical analyses of the primary endpoint will be done with a two-sided significance level of 5 %. The statistical analyses of the secondary endpoints are exploratory. A separate analyses will be performed for each group (“RISK” and “LOW RISK”). In addition to the intention-to-treat analyses a secondary per protocol analyses will be done including all patients who were treated according to the originally assigned treatment arm without protocol violations (= unjustified dose modification, therapy delay and/or improper switch to another therapy within the first 12 months).

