**Figure 7: Boundaries for deaths within 12 weeks**

Simulations show that with this boundary the risk to wrongly conclude that there is an excess of early deaths (whereas the real event rate is below or equal to 10%) is 13%. On the other hand, the power to detect an excess of early deaths of 15% or more will be 78%.

If we find significant differences in toxicities or if the number of early deaths observed, reaches the boundary defined by the sequential plan, a full analysis will be performed, and the results will be discussed among the members of the study committee together with the independent biometrical reviewers. The study committee together with the independent biometrical reviewers will decide, whether and how the study will proceed.

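### The Group 1 toxicity rule in 16.6 (repeated Fisher tests with a Pocock correction) has no stated looks, direction or power, and runs well below its stated 5%, so sensitivity is low unless the excess is large

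*Protocol*

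**What the plan says.** Section 16.6 sets stopping rules for Group 1 only. For toxicity it states: "Interim analyses on severe organ toxicity (WHO score grade III-IV) within the first 12 weeks of therapy will be performed twice a year". The rates "of both treatment arms will be compared by Fisher’s exact test", and "A group sequential design according to Pocock will be applied to account for repeated significance testing to assure an overall significance level of" 5%.

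The text below Figure 7 gives the trigger: "If we find significant differences in toxicities or if the number of early deaths observed, reaches the boundary defined by the sequential plan". Crossing leads to a full analysis, after which the study committee decides with the independent biometrical reviewers how to proceed. Nothing stops automatically.

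The section does not give the number of looks, the direction of the test, the toxicity rate expected in Arm A, the excess to be detected or the power. The early-death rule beside it has an acceptable rate (10%), an unacceptable rate (15%), a false-alarm risk (13%) and a power (78%).

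On sidedness, section 16.3 says only: "The statistical analyses of the primary endpoint will be done with a two-sided significance level of 5"%. That covers the primary endpoint, not toxicity.

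**The concern.** The protocol itself fixes the test, the boundary shape, the overall level and a calendar schedule. How that combination performs can be worked out, and the section does not report it.

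Three features work against sensitivity. A Pocock boundary with many looks sets a strict threshold at each one. Fisher's exact test is conservative at small counts, and its discreteness is felt at every look. If the test is two-sided, half of the error is spent on Arm A being the more toxic arm, although Arm B adds MTX to the same PDN and VBL backbone.

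Pocock's constant also needs a number of looks set in advance, and a twice-yearly schedule in a trial of uncertain length does not supply one.

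At stake is how readily the randomised comparison would flag an excess of severe toxicity. Section 16.6 says that drug toxicity and disease-related organ dysfunction are hard to tell apart in the individual patient. That makes the comparison between arms particularly useful.

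**Working it through.** **Inputs from section 16.5.1.** "we expect to reach the maximum sample size of 228 evaluable patients after a period of approximately 6 years". The expected size under the alternative is 158, and "If the alternative hypothesis is true, this will be 4.7 years". Under the null the duration is 4.3 years. With 1:1 allocation (assumed; no ratio is given), 228/2 = 114 and 158/2 = 79 per arm.

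**Number of looks.** 2 × 6 = 12; 2 × 4.7 = 9.4; 2 × 4.3 = 8.6. So about 9 to 12.

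**Calibration.** For the primary endpoint (50% v 30%, 202 patients), exact Fisher power at 101 per arm is 79.9%, so the plan's sample size reproduces.

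**Nominal level.** For K equally spaced looks, choose c so that P(max |Z_k| ≥ c) = 0.05 under the null, with Corr(Z_j, Z_k) = √(j/k) for j ≤ k. The level per look is 2(1 − Φ(c)).
- K = 12: c ≈ 2.59, nominal p ≈ 0.0097.
- K = 9: c ≈ 2.54, nominal p ≈ 0.0112.

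**First look by hand.** 228/12 = 19 patients, so 9 or 10 per arm.
- With 9 per arm, 0 v 6 events gives p = 2 × C(9,6)/C(18,6) = 2 × 84/18,564 = 0.0090, which crosses.
- With 10 per arm, 0 v 6 gives 2 × 210/38,760 = 0.0108, which does not cross, so 0 v 7 is needed.

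**Actual overall level.** This was simulated with 40,000 trials per scenario, equal increments and a two-sided Fisher test at each look. With 12 looks and 114 per arm it is 0.7% at a common rate of 5%, 1.6% at 10%, 2.4% at 20% and 2.7% at 40%. With 9 looks and 79 per arm it is 0.4% to 2.7%. The stated 5% is therefore kept only as an upper bound. A z-test on the same boundary gives about 4.5-5.2% at rates of 20% or more, so there the shortfall comes from Fisher's discreteness.

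**Detection.** The Arm A rate is assumed, because the protocol gives none. The last column is a one-sided mid-p test at an overall 5% on a Pocock-shaped boundary (nominal p about 0.0106 at 12 looks).

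| Arm A v Arm B | Current rule, 12 looks, 114/arm | Current rule, 9 looks, 79/arm | One-sided mid-p, 12 looks, 114/arm |
|---|---|---|---|
| 5% v 10% | 11% | 7% | 26% |
| 10% v 20% | 33% | 22% | 52% |
| 15% v 30% | 58% | 40% | 74% |
| 20% v 30% | 23-24% | 15-17% | 40% |
| 20% v 35% | 51-52% | 36% | 69% |
| 20% v 40% | 78% | 59% | 89% |

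For 10% v 20% the gain splits as follows: a one-sided Fisher test raises detection from 33% to 45%, and mid-p raises it from 45% to 52%. False alarms under the mid-p rule are about 2% at a common rate of 5% and about 4% at 20% to 40%.

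**Can the looks exceed 12?** Section 16.5.1 expects 35-40 randomisations a year and says: "We assume that we will not be able to evaluate response at week 12 in 10 % of the patients". So 228/(0.9 × 40) = 6.3 years and 228/(0.9 × 35) = 7.2 years, or about 13 to 14 looks.

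**The case against.** Much of the opposing case stands.

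- **Missing doublings.** A reader might infer that the rule misses most doublings of severe toxicity. That depends on an Arm A rate the protocol does not give. At 114 per arm it holds below a baseline of about 13%; above that, most doublings are flagged. Section 2 reports severe cytopenia and hepatic dysfunction in LCH I only with initial risk-organ involvement, so a high baseline in Group 1 cannot be excluded.
- **The 5% level.** A reader might infer that the error rate is out of control. It is not: the actual level lies below 5%, so the bound is respected. The cost is sensitivity.
- **Unnoticed toxicity.** A reader might infer that the trial simply runs on unless this test is significant. The DSMB reviews toxicity reports twice a year (section 15), serious events are reported by the next working day and relayed to the DSMB (9.5.1), and early deaths have their own sequential rule. None of these compares toxicity between arms against a criterion, but they are real safeguards.
- **Proof of tolerability.** Nothing in the protocol treats a non-significant result as evidence that MTX is tolerable. Toxicity is a secondary endpoint and its analysis is exploratory.
- **Sidedness and detail.** Two-sided testing is an assumption for toxicity. A one-sided Fisher rule at 5% would still detect 10% v 20% in only 45% of trials. Sidedness and a boundary table could be left to an analysis plan; the poor performance follows from the test, boundary and schedule already fixed here.
- **Number of looks.** A constant set for 12 looks remains valid if the trial ends sooner. One or two extra looks would hardly push a level below 3% above 5%. This is an operational gap, not an inflation problem.
- **Sample size.** A single uncorrected Fisher test at 114 per arm has only 50% power for 10% v 20%. Part of the limit is the rarity of the disease.

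**Conclusion.** The concern holds in a limited form. As specified, the toxicity rule is conservative: nominal level about 0.01 per look, actual overall level below 3%. Its sensitivity is low for a 10-point excess, at about 33% for 10% v 20% and 23-24% for 20% v 30% with 114 per arm, and lower with 79. It is adequate only for large excesses such as 20% v 40%. The section reports none of this, in contrast to the early-death rule next to it.

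The figures assume 1:1 allocation, a two-sided test, equally spaced looks continued to the stated size, and the baseline rates shown. The finding does not mean that the trial is unmonitored or that its error control fails. It is a worthwhile and inexpensive improvement to the only formal comparative toxicity criterion used during the trial.

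**What to change.** In section 16.6, keep the overall 5% and change three things:

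1. Make the rule one-sided for excess toxicity in Arm B.
2. Replace Fisher's exact test with a mid-p or score test.
3. Replace the fixed-look Pocock constant with a Pocock-type error-spending function indexed by patients evaluated, so that any number of twice-yearly looks is valid.

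Then state the false-alarm rate and power over a range of Arm A rates, as is done for early deaths. The improved figures above use equally spaced looks with a Pocock-shaped boundary, so they should be recomputed for the spending function chosen.

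The cost is a rewording and a new boundary table, with no extra patients, visits or data. False alarms in the harm direction rise from about 0.4-1.4% (half of 0.7-2.7%) to about 2-4%, and each leads only to the full analysis already described. There would be no formal boundary for excess toxicity in Arm A. A more liberal level such as 10% is an option for the DSMB to consider; it is not needed to correct the rule.

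### Section 16.6 monitors early deaths to week 6 but takes its benchmark, 10% limit and boundary from deaths to week 12; on a literal 6-week count the stated 78% power does not apply to a 15% 12-week death rate

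*Protocol*

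**What the plan says.** Protocol 16.6 sets up two safety rules for patients with risk organ involvement: one for severe organ toxicity and one for early death. The statements on early death are these:

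- The count: "In addition we will monitor early deaths within the first 6 weeks of therapy".
- The benchmark, from arm A of LCH II: "5 early deaths within 12 weeks of therapy were observed among 50 patients", which is 10%.
- The acceptable rate: "Based on this previous experience, we consider an early death rate below or equal to 10% as acceptable".
- The unacceptable rate: "An early death rate of 15% as unacceptably high". This sentence names no window of its own.
- The method: "We will perform Wald’s sequential ratio test", with upper boundaries shown in Figure 7.
- The figure caption: "Boundaries for deaths within 12 weeks".
- The operating characteristics, from simulation: a 13% risk of a false alarm at a true rate of 10% or less. For a true rate of 15%, "the power to detect an excess of early deaths of 15% or more will be 78" percent.

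Reaching the boundary leads to a full analysis and a discussion by the study committee with the independent biometrical reviewers. It does not stop the trial automatically.

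**The concern.** The sentence that tells the trial team which deaths to count uses 6 weeks. The benchmark, the limit explicitly based on it and the boundary caption use 12 weeks. Whoever runs the rule has to choose between the two.

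The choice matters because the error goes in one direction. A boundary built for deaths over 12 weeks expects more deaths than occur in 6. Feeding it the shorter count can only delay or prevent a signal. Deaths in weeks 7 to 12, when course 2 is given (9.1.1.2 and 9.1.2.2), would be left out. This is the only formal mortality boundary for Group 1, and a reader would take its 78% power at face value.

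**Working it through.** **Inputs.** From 16.6 and Figure 7: p0 = 0.10, p1 = 0.15, Wald's sequential test with an upper boundary, stated false alarm 13%, stated power 78%. From 16.5.1: 202 patients (fixed design) and 228 (group sequential maximum), tried as truncation points. Figure 7 itself is not shown, so the boundary's intercept was chosen to match the stated false-alarm rate. The count is checked after every patient.

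**Boundary.** Signal when the number of deaths S_n among n patients satisfies

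S_n ≥ [a + n·ln(0.90/0.85)] / ln[(0.15 × 0.90)/(0.10 × 0.85)] = (a + 0.0572n)/0.4626.

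With a = 1.64 this is S_n ≥ 3.54 + 0.1236n. At n = 202 it is 3.54 + 24.96 = 28.50, so 29 deaths.

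**Reproducing the plan's figures.** Exact binomial recursion along the path, truncated at 202 patients:

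| True rate of the counted event | Probability of crossing | Plan states |
|---|---|---|
| 10% | 13.1% | 13% |
| 15% | 78.1% | 78% |

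A boundary with nominal errors of 0.15 and 0.20, a = ln(0.80/0.15) = 1.67, gives 12.6% and 77.7%. So the stated figures fit 10% and 15% limits applied to the event for which the boundary was built.

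**Counting only deaths to week 6.** Let the true 12-week rate be 15% and let f be the share of those deaths that fall by week 6. The counted rate is 0.15f. The protocol gives no value for f, so a range is shown (a = 1.64, N = 202):

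| f (assumed) | 6-week rate | Expected count in 202 | Probability of crossing |
|---|---|---|---|
| 100% | 15.0% | 30.3 | 78% |
| 90% | 13.5% | 27.3 | 59% |
| 80% | 12.0% | 24.2 | 37% |
| 70% | 10.5% | 21.2 | 18% |
| 60% | 9.0% | 18.2 | 6% |
| 50% | 7.5% | 15.2 | 2% |

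A constant hazard over the 12 weeks gives a 6-week rate of 1 − 0.85^0.5 = 7.8% and a crossing probability of about 2%.

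**Sensitivity.** With a = 1.67 and N = 228 the probabilities for f = 90% down to 50% are 62%, 38%, 18%, 6% and 2%. The truncation point hardly changes the result.

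**The case against.** **It may be a slip in one phrase.** The benchmark, the caption, the toxicity rule in the same paragraph and the primary endpoint (16.2.1.1, which counts death within 12 weeks) all use 12 weeks. If 12 weeks was intended, the 13% and 78% stand and no power is lost. This is a fair reading and probably the likelier one. It does not remove the contradiction, because the odd phrase sits in the sentence that defines the count.

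**The 15% limit names no window.** If it was meant as a 6-week rate, the boundary keeps its 78% power for that rate. The 10% limit would then lack a 6-week benchmark, so the text would still need correction.

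**Later deaths are not unseen.** Every death must be reported by the next working day and is relayed to the DSMB (9.5.1). Death within 12 weeks is part of the primary endpoint, which is compared between arms at five analyses (16.4.1). This limits the harm, but it does not give the boundary the power stated for it.

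**Two stronger readings go too far.** A reader might infer that the rule will hardly ever trigger. That holds only if about 60% or fewer of the deaths fall by week 6, and the documents say nothing on timing.

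A reader might also infer that the 13% and 78% fit only a count pooled over both arms, so that an excess confined to arm B would be diluted. The figures do not establish this. With each arm followed separately to 228/2 = 114 patients and an alarm if either crosses, the probability is 1 − (1 − x)², where x is one arm's crossing probability. Checked every 5 patients per arm this gives 13.4% and 77.8%; every 12 patients, 12.8% and 77.8%. Both round to the stated values. The text does not say whether the count is pooled or per arm, and Figure 7 is not shown, so no criticism can rest on a pooled design.

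**Conclusion.** The contradiction is certain: 16.6 sets a 6-week count against a benchmark, a 10% limit and a boundary for 12 weeks. The boundary's stated properties are sound for the event it was built on.

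The consequence is conditional. If the 6-week sentence is followed literally and 15% is read as a 12-week rate, power is below 78% for any share under 100%: about 59% when 90% of the deaths fall by week 6 and about 2% when half do. This rests on three assumptions: the share itself, a boundary reconstructed from the stated error rates, and a single count truncated at 202 or 228 patients. The direction of the loss does not depend on them, since a shorter window cannot count more deaths.

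The point deserves correction before the rule is used, because it concerns the stated properties of a mortality rule and costs little to settle.

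**What to change.** Reconcile the monitoring sentence in 16.6 with the benchmark and the Figure 7 caption, so that one death window applies throughout.

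- If 12 weeks is meant, as the benchmark, the caption and the primary endpoint suggest, correct the monitoring sentence. The stated 13% and 78% then apply unchanged.
- If 6 weeks is meant, derive the acceptable and unacceptable rates from 6-week deaths, redraw the boundary, and restate the false-alarm risk and power for that window.
- In either case, state the window in the sentence that gives the 15% limit.

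The first route costs one sentence. The second also needs a 6-week death rate from LCH II, which the protocol does not report, and a rerun of the simulation. Neither needs more patients.

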## 16.2 ENDPOINTS

### 16.2.1 Primary endpoints

#### 16.2.1.1 Group 1 “RISK” patients:

The primary aim of the study is to compare the therapeutic efficacy of **control arm A** (PDN+VBL) with the **experimental arm B** (PDN+VBL+MTX). The primary endpoint is

the proportion of **non-responder in risk organs to the initial treatment.**

**Non-response** to initial therapy is defined as:

- death within 12 weeks of initial treatment or
- progression (worse) in risk organs at week 6
- lack of response (=intermediate response or progression) in risk organs at week 12 as compared to the status of disease at week 6

If the null hypothesis is true, the two randomized treatment arms are equally effective in terms of non-response. If the alternative hypotheses is true, there is a difference between the two randomized arms in terms of efficacy.

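### Section 16.6 counts early deaths over 6 weeks, but its reference rate, 10%/15% limits and Figure 7 boundary are for 12 weeks; the two windows must be reconciled

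*Protocol*

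**What the plan says.** Section 16.6 of the protocol sets stopping rules for organ toxicity and early deaths, only for patients with risk organ involvement. On deaths it defines the count: "In addition we will monitor early deaths within the first 6 weeks of therapy". The rest of the rule is written for another window:

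- Reference rate, from arm A of LCH II: "5 early deaths within 12 weeks of therapy were observed among 50 patients", that is 10%.
- Limits, said to be based on that experience: "we consider an early death rate below or equal to 10% as acceptable"; "An early death rate of 15% as unacceptably high".
- Method: "We will perform Wald’s sequential ratio test", with an upper boundary in Figure 7.
- Caption of Figure 7: "Boundaries for deaths within 12 weeks".
- Operating characteristics quoted for that boundary: 13% risk of a false alarm at a rate of 10% or less, and 78% power at 15% or more.

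Two neighbouring definitions also use 12 weeks: the severe-toxicity comparison in section 16.6, and the death component of the Group 1 primary endpoint in section 16.2.1.1 ("death within 12 weeks of initial treatment or").

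**The concern.** A sequential boundary has its stated error rates only if the event counted is the event whose rates were used to build it. Here the counting sentence names deaths in weeks 1-6, while the rates of 10% and 15% describe deaths in weeks 1-12. Followed literally, every death in weeks 7-12 is left out, yet the total is judged against a line that expects those deaths. The error can only run one way, towards missing an excess. Two analysts could also apply different windows to the same deaths and disagree on whether the boundary was reached. Reaching it is what triggers the full analysis described under Figure 7.

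**Working it through.** **Inputs.** From section 16.6: p0 = 0.10, p1 = 0.15, Wald's sequential test, upper boundary, stated results 13% and 78%. From section 16.5.1: 202 patients (fixed design) and 228 (group sequential maximum). Not stated: the nominal alpha and beta of the Wald test, the number of patients at which it is truncated, and whether deaths are pooled over arms. Figure 7 itself is not available, so these were inferred by matching the stated results, with a pooled count.

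**Step 1: the boundary.** Each death adds ln(0.15/0.10) = 0.4055 to the log likelihood ratio. Each survivor adds ln(0.85/0.90) = -0.0572. The rule signals when the sum reaches ln((1 - beta)/alpha). With nominal alpha 0.15 and beta 0.20 this is ln(0.80/0.15) = 1.674. Solving for the number of deaths d among n patients:

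d ≥ (1.674 + 0.0572 n)/(0.4055 + 0.0572) ≈ 3.62 + 0.1236 n

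This gives 10 deaths at n = 50 and 29 deaths at n = 202.

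**Step 2: reproduce the plan's figures.** An exact binomial recursion over n = 1 to 202, upper boundary only, gives a crossing probability of 12.6% at a rate of 10% and 77.7% at 15%. These round to the stated 13% and 78%. The same line run to 228 patients gives 13.2% and 81.3%. So the stated characteristics belong to an event that occurs at rates of 10% and 15%, and the protocol defines the 10% as a 12-week rate.

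**Step 3: count only weeks 1-6 against the same line.** If a share f of the 12-week deaths falls in weeks 1-6, the event probability becomes f times the 12-week rate. The protocol does not give f, so a range is shown (202 patients).

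| Assumed share f | Expected deaths counted at a 15% 12-week rate (202 × 0.15 × f) | Chance of a signal, 12-week rate 15% | Chance of a signal, 12-week rate 20% |
|---|---|---|---|
| 100% | 30.3 | 78% | 99% |
| 90% | 27.3 | 58% | 97% |
| 80% | 24.2 | 36% | 87% |
| 70% | 21.2 | 17% | 65% |
| two thirds | 20.2 | 13% | 56% |
| 50% | 15.2 | 2% | 13% |

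The two-thirds row can be checked by eye: 0.15 × 2/3 = 0.10, so the chance of a signal equals the designed false-alarm risk. With 228 patients the 15% column reads 81%, 62%, 38%, 18%, 13% and 2%, the same pattern.

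**Step 4: how patients enter a 12-week count.** If each death is entered at once and each survivor only on completing 12 weeks, deaths run ahead of the survivors who belong with them. A simulation with 202 patients, 37.5 randomisations a year (the middle of the 35-40 in section 16.5.1) and deaths assumed uniform over 12 weeks puts the false-alarm risk at about 16%. Entering the same patients in order of randomisation, with the window complete, gives about 12.5%.

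**The case against.** The strongest reply is that the 6 weeks is a slip. The reference rate, the limits, the caption, the toxicity window and the primary endpoint all say 12 weeks, and a team plotting deaths on a figure labelled for 12 weeks would probably count 12-week deaths. That is plausible, and on that reading the 13% and 78% stand. But the sentence at fault is the one that defines what is counted, and nothing else in the protocol corrects it.

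A reader might infer that the rule would rarely signal an unacceptable death rate. The documents do not support that as a general statement. It depends on an unstated share: at a 90% share the power at 15% is still 58%, and at a true 12-week rate of 20% the rule signals in 87% of trials with an 80% share.

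A reader might also infer that RISK patients would be left without any mortality safeguard. That is not so. Under section 9.5.1 every death is reported by the next working day and relayed to the data safety monitoring board, which under section 15 monitors the study on ethical and scientific grounds. Deaths within 12 weeks also enter the primary endpoint, which is looked at five times, though as a comparison of arms. Crossing the Figure 7 line leads to a full analysis and discussion, not to an automatic stop.

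Finally, the boundary is inferred. If the line were applied to one arm of 101 patients, it would give about 9% and 53% even with matching windows. The percentages in the table are therefore illustrative; the direction of the loss is not in doubt.

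**Conclusion.** The contradiction between a 6-week count and 12-week limits and boundary is explicit and unreconciled, so the early-death rule is wrong as written. If weeks 1-6 alone are counted, power against a 15% 12-week death rate is below the stated 78% by an amount the protocol cannot settle: a moderate loss if nearly all early deaths fall in weeks 1-6, an almost complete one if they are spread evenly. The figures assume a pooled count, truncation at 202 patients and nominal alpha and beta of 0.15 and 0.20, chosen because they reproduce the stated 13% and 78%. This is the only formal boundary on the early-death rate in the group for which stopping rules were judged necessary, so it should be corrected before use.

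**What to change.** Reconcile section 16.6 and Figure 7 so that count, limits and boundary use one window. There are two consistent ways:

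1. State the count as deaths within the first 12 weeks of therapy. This matches the existing reference rate, limits and Figure 7, and the stated 13% and 78% stay.
2. Keep a 6-week count, and derive the acceptable and unacceptable rates, the boundary, the false-alarm risk and the power again from 6-week data.

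In either case say how patients enter the count. To keep the stated 13%, evaluate patients in order of randomisation once their window is complete. If deaths are to count at once, recalibrate the boundary for that. Stating the nominal alpha and beta, the number of patients covered, and whether the count is pooled or per arm would let others reproduce the rule.

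The first option changes one phrase and adds a sentence on entry order; it needs no new data, because deaths are already reported by the next working day. The second needs a 6-week death rate from LCH II, which the protocol does not give, and a new Figure 7.
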